Immunodetection: Serial 4 µM sections of skin biopsy sections are deparaffinized, hydrated, and serially incubated in citrate buffer, H₂O₂, blocking solution, primary antibody, and appropriate secondary antibody, with intervening washes. The ABC biotin/avidin method with Nova Red substrate is utilized for immunodetection (Vector Labs). Primary antibodies include: total Akt (Cell Signaling), phospho-specific Akt (Ser 473, Cell Signaling), total eNOS (Transduction Labs), and phospho-specific eNOS (Ser 1177, Cell Signaling). When available, blocking peptide is incubated with primary antibody in a separate section to ensure specificity of staining. If blocking peptide is not available, additional sections are incubated without primary antibody. To ensure localization of identified signal in vascular cells, additional sections will be processed for immunofluorescence and colocalization with primary antibodies directed against the endothelium-specific von Willebrand factor (Santa Cruz Biotechnology). Images will be viewed using an AX70 Olympus Microscope with Phase 3 Imaging System (Image Pro 4.0 software) or the Zeiss LSM-410 Invert Laser Scan confocal microscope with imaging software (Matrox Image-Series Utilities).

Assays for markers of inflammation, insulin, free fatty acids

Plasma samples from insulin resistant and healthy subjects will be assayed for high sensitivity CRP (hsCRP), tumor necrosis factor-α (TNF-α), and interleukin-6 (IL-6) using the respective ELISA kits (Sigma; Endogen, Woburn, MA; BenderMedSystems; Vienna, Austria). Plasma insulin concentration will be measured using an Immunoenzymatic Sandwich Assay (Beckman Coulter, Inc.). Acrylodan-labeled Intestinal Fatty Acid Binding Protein (ADIFAB), a fluorescent molecule, will be used to assay the concentration of free fatty acids. The assay is accurate to about 1nM (72). All assays will be performed in duplicate by investigators blinded to the status of the subject (metabolic syndrome or control) and treatment.

BIOSTATISTICAL ANALYSIS

Statistical Analysis

Sample size calculation: All specified protocols employ a randomized, placebo-control cross-over design. Given the paired-design, the sample sizes have been calculated using estimates of the difference in flow-mediated, endothelium-dependent vasodilation after placebo and active treatment.

Table 2: Calculated Power For a Given Effect Size and Standard Deviation
Standard Deviation

Treatment Effect	3.5%	4.0%	4.5%
2.5%	.97	.91	.84

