3.0%	.99	.98	.94
3.5%	1.0	.99	.98

endothelium-dependent vasodilation (i.e., the change in brachial artery vasodilation) between active therapy and placebo, will be assessed using repeated measures ANOVA (73). All analyses will employ the intention-to-treat principle. The treatment “order effect” will be explored by examining the interaction between treatment group (e.g. acipimox vs. placebo) and sequence of treatment (placebo first vs. active therapy first).

Baseline characteristics of treatment and control patients will be compared using Student’s t-test or non-parametric tests, depending on the distribution of the data. To examine whether the active therapy has similar effects on flow-mediated vasodilation between healthy subjects and those with the metabolic syndrome, we will test the interaction between treatment group and the metabolic syndrome (yes/no). In secondary analyses, we will assess the effects of active therapy on eNOS phosphorylation, insulin sensitivity, and plasma inflammatory markers such as CRP, IL-6, and TNF- α . We will assess the relationship between the change in eNOS phosphorylation and changes in endothelium-dependent vasodilation using linear regression analyses, controlling for age, and gender. Likewise, we will examine the relationship between changes in insulin-mediated vasodilation and insulin-sensitivity associated with active treatment. Multiple analysis of variance (MANOVA) will be used to examine the main and interaction effects of categorical variables on multiple dependent variables, and multiple analysis of covariance (MANCOVA) for continuous independents. Thus, in the analyses, we can include vascular function and other outcomes simultaneously as dependent variables in the models. If the dependent variables are uncorrelated with each other, repeated measure ANOVA for each dependent variable will be employed.

Data interpretation: Vascular function will be determined after each intervention. Each intervention will be studied individually. If flow-mediated vasodilation is restored after an intervention (acipimox) compared with placebo, it will be interpreted that FFA impairs endothelial insulin signaling and decreases endothelium-dependent vasodilation. This interpretation will be confirmed by cutaneous tissue testing. If eNOS serine₁₁₇₇ phosphorylation is increased after an intervention compared to placebo, it will be interpreted that improved activation of the PI3-kinase

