Based on previous studies, we expect to find an absolute difference in flow-mediated, endothelium-dependent vasodilation of the brachial artery between the test agent and placebo of 3% with an estimated standard deviation of 4% (68). With a 2-sided alpha error of 0.05 and a power of 90%, 30 subjects in each group of each protocol should find at least this difference in the primary endpoint (Table 2).

Statistical methods: All descriptive data will be expressed as means \pm standard deviation. The primary endpoint of change in flow-mediated,

pathway increases eNOS phosphorylation and resultant NO production. This interpretation will be supported if multivariate linear regression analysis defines a significant positive relationship between changes in eNOS phosphorylation and vascular and/or skeletal muscle metabolic function. If endothelium-dependent (flow-mediated) or insulin-mediated vasodilation remains similar despite an intervention (acipimox), it will be interpreted as a lack of effect of the agent on endothelial-insulin signaling and vascular function. If any intervention increases vasodilation to nitroglycerin, it will be interpreted that the intervention has improved vascular smooth muscle function. If the intervention improves vascular function in both subjects with the metabolic syndrome and healthy subjects, this will be interpreted as a generalized effect, independent of the metabolic syndrome.

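### The regression of FMD change on eNOS change has no metabolic-syndrome term, so if the two groups are pooled, a group difference in both changes can pass as support for the mechanism

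*Combined protocol and SAP*

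**What the plan says.** All references are to the Biostatistical Analysis section of the combined protocol and SAP.

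- **Covariates.** Under Statistical methods, the change in eNOS phosphorylation is related to "changes in endothelium-dependent vasodilation using linear regression analyses, controlling for age, and gender". No other covariate is listed, and the analysis set is not stated.
- **Second regression.** The next sentence reads "Likewise, we will examine the relationship between changes in insulin-mediated vasodilation and insulin-sensitivity associated with active treatment". It has no covariate list of its own; its opening word may carry over age and gender.
- **Where group does appear.** For the effect of treatment on FMD, "we will test the interaction between treatment group and the metabolic syndrome (yes/no". The indicator is named there and not in either regression.
- **Use of the slope.** Under Data interpretation, a rise in eNOS phosphorylation on active treatment is first read as activation of the pathway. Then: "This interpretation will be supported if multivariate linear regression analysis defines a significant positive relationship between changes in eNOS phosphorylation" and vascular or skeletal-muscle metabolic function. Covariates are not named here either.
- **Other models.** MANOVA "will be used to examine the main and interaction effects of categorical variables on multiple dependent variables". Metabolic syndrome is not named as one of those variables, and the sentence is not tied to the regressions.
- **Size.** "With a 2-sided alpha error of 0.05 and a power of 90%, 30 subjects in each group of each protocol should find" a 3% absolute FMD difference with an SD of 4%.

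**The concern.** The trial enrols two groups chosen to differ, and the plan allows that the drug may act differently in them, since it tests that interaction. If acipimox raises both eNOS phosphorylation and FMD more in metabolic syndrome than in healthy subjects, a pooled scatter plot shows two clouds, one above and to the right of the other. A line fitted through both slopes upward even if, inside each cloud, subjects with a larger eNOS change have no larger FMD change. Anything else that separates the groups would give the same picture.

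At stake is the supporting step of the mechanistic argument. The rule asks only for a significant positive slope, and a pooled slope could meet it because the groups differ. What would then be missing is an association between subjects within a group. Each subject contributes one pair of changes, so no version of this regression can show a within-subject link.

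**Working it through.** **1. The plan's own figure and the SD scale.** Inputs: effect 3%, SD 4%, n = 30, two-sided alpha 0.05 (Sample size calculation and Table 2). For a paired t-test the noncentrality is (3/4) × √30 = 4.11 on 29 df, which gives power 0.978; Table 2 prints 0.98. All nine cells of Table 2 agree with this method to within 0.01. A two-sample formula with 30 per arm gives 0.83 for the same cell and does not fit. So the 4% acts as the SD of the within-subject difference between acipimox and placebo, which is the FMD change used in the regression. A 3-point group gap in that change is 3/4 = 0.75 SD.

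**2. Slope with no association inside either group.** Let the mean eNOS change differ between the groups by dX and the mean FMD change by dY, both in within-group SDs. With equal groups, pooling adds dX·dY/4 to the covariance and dX²/4 and dY²/4 to the variances:

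- slope b = 0.25·dX·dY / (1 + 0.25·dX²)
- correlation r = 0.25·dX·dY / √[(1 + 0.25·dX²)(1 + 0.25·dY²)]

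At dX = dY = 0.5: 0.0625/1.0625 = 0.06. At 0.75: 0.1406/1.1406 = 0.12. At 1.0: 0.25/1.25 = 0.20. If either gap is zero, b = 0. If the gaps have opposite signs, b is negative.

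**3. Hand check of the error rate at 0.75 SD.** With 60 subjects and four coefficients there are 56 df. The expected t is about 0.123 × √56 / √(1 − 0.123²) = 0.93, and the critical value is 2.00. The chance of exceeding it is about 1 − Φ(1.07) = 14%.

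**4. Simulation.** 30 + 30 subjects, zero association within each group, FMD change regressed on eNOS change, age and gender, 10,000 trials per row. Age and gender are unrelated to group. All gaps are assumptions.

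| dX (eNOS) | dY (FMD) | FMD gap in points (dY × 4) | Significant positive slope, no group term |
|---|---|---|---|
| 0.5 | 0.375 | 1.5 | 5.1% |
| 0.5 | 0.5 | 2 | 6.7% |
| 0.5 | 0.75 | 3 | 9.2% |
| 0.75 | 0.75 | 3 | 14.6% |
| 1.0 | 0.75 | 3 | 21.6% |
| 1.0 | 1.0 | 4 | 33.1% |
| 1.5 | 0.75 | 3 | 36.4% |
| 0.75 | 0 | 0 | 2.6% |
| 0 | 0.75 | 3 | 2.8% |
| 0.75 | −0.75 | −3 | 0.2% (slope negative) |

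The nominal rate is 2.5%, with a simulation error of √(0.025 × 0.975/10,000) = 0.16 points. With a metabolic-syndrome term the rate is 2.2% to 2.9% throughout.

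**5. Can age stand in for group?** If mean age also differs by 1 SD between the groups, the rate falls from 14.6% to 11.5% at gaps of 0.75/0.75, and from 21.6% to 16.4% at 1.0/0.75. Age adjustment then removes part of the bias, but not most of it.

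**The case against.** **Pooling is not stated.** This is the strongest point. The sample size is set per group, Table 2 reproduces as a paired test within one group of 30, and Data interpretation considers the two kinds of subject separately. Regressions within each group would be compatible with the text and would have no such bias. A reader might infer that the plan commits to a pooled fit; it does not. But one model with one covariate list most naturally reads as one fit, no within-group fit is described, and an analyst following the list literally on all subjects would leave group out.

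**The plan predicts no group gap.** It gives a single 3% effect, and testing an interaction does not forecast one. This stands: the gaps above are scenarios. A 3-point FMD gap already means the full planned effect in one group and none in the other, and the matching eNOS gap has no source in the documents. A reader might cite the rate of about 84% that arises at 1.5 SD in both changes. That needs a gap of 1.5 × 4 = 6 points, twice the planned effect, and nothing in the plan supports it.

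**Both regressions may seem to carry the conclusion.** They do not. The support rule concerns eNOS changes. No stated decision rests on insulin-mediated vasodilation against insulin sensitivity.

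**The regression is only supporting evidence.** Correct. The eNOS reading starts from the randomized comparison with placebo. A false slope would strengthen the mechanistic claim wrongly, but would not create a drug effect.

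**A group term discards signal.** If eNOS is the route, larger changes in both measures in one group are part of what it predicts. That is a real cost. But with two groups the between-group contrast is one comparison, which any other group difference explains equally well.

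**Conclusion.** The concern holds in a limited form. The covariate list for the eNOS regression omits metabolic syndrome, the plan does not say how the two groups are handled, and a significant positive slope is given evidential weight. Under pooling, with both changes differing by group in the same direction and no association inside either group, the false positive-slope rate is about 7%, 15% and 33% at equal gaps of 0.5, 0.75 and 1 SD, against 2.5%. These figures assume 30 + 30 subjects and complete pairs of changes. Even at 1 SD, about two trials in three would not show the false slope.

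The documents do not support the further inference that the mechanism would be declared on confounding alone, nor that adjusting for age and gender never helps. The point touches a secondary analysis. It is worth correcting because the variable is already collected and the change costs little.

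**What to change.** 1. State the analysis set for the regression of FMD change on eNOS change, and add metabolic syndrome (yes/no) to age and gender. The slope is then the common within-group slope.
2. Report the slope with its confidence interval in each group as well, so that a reader can see whether one group drives the result.
3. In Data interpretation, make the support rule refer to the group-adjusted slope, for every regression on eNOS change that the rule uses, including those on skeletal-muscle metabolic function.
4. For consistency, list the covariates of the regression of insulin-mediated vasodilation on insulin sensitivity and include the same group term.

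The group term takes the residual degrees of freedom from 60 − 4 = 56 to 60 − 5 = 55. The substantive cost is that covariation between the groups no longer counts toward the mechanism; it can still be shown descriptively. No new data are needed.

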Title: The Impact of Free Fatty Acid Reduction on Vascular Function in the Metabolic Syndrome

NCT00759291

Document Date: February 28, 2008

STUDY PROCEDURES AND PROTOCOL

This study uses a randomized, placebo-controlled crossover design.

After providing informed consent, both groups will undergo an initial screening visit in the Vascular Medicine Research Center. This visit will include a comprehensive health history and physical exam and anthropomorphic data collection (height, weight, body mass index (BMI) and waist-hip ratio). Screening blood tests will be drawn to assess fasting glucose, blood count, lipid profile, glycosylated hemoglobin, and assessment of renal and hepatic function. Baseline serum insulin and nonesterified free fatty acid levels will also be drawn at this visit. An ECG will be performed.

We hypothesize that acipimox, by decreasing plasma FFA concentrations, will augment endothelium-dependent vasodilation in conduit vessels and insulin-mediated vasodilation in forearm resistance arterioles *in vivo*, whole-body insulin sensitivity, and AKT and eNOS phosphorylation in skin biopsy specimens *ex vivo*, when compared with placebo.

Subjects will be studied at 2 separate visits, 4 weeks apart, in a randomized, double-blind crossover design. Subjects will receive either acipimox 250 mg tablets orally every 6 hours, or matching placebo, for 7 days prior to and at 7 am on the morning of the study visit. Each visit will include vascular function testing and a forearm skin biopsy. Forearm blood flow will be measured in the basal state, and with insulin infusion.

Evaluation of vascular function in conduit vessels:

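### A gain in flow-mediated dilation on acipimox would be credited to free fatty acids without a check that they fell

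*Combined protocol and SAP*

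**What the plan says.** The hypothesis in Study Procedures and Protocol runs through FFA: acipimox, "by decreasing plasma FFA concentrations, will augment endothelium-dependent vasodilation in conduit vessels". The Data interpretation paragraph turns that into a rule for a positive result: "If flow-mediated vasodilation is restored after an intervention (acipimox) compared with placebo, it will be interpreted that FFA impairs endothelial insulin signaling". The only check attached to the rule is testing of the skin biopsy.

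FFA is drawn at screening, before treatment. The section on assays for inflammation, insulin and free fatty acids also describes an FFA method and adds: "All assays will be performed in duplicate by investigators blinded to the status of the subject (metabolic syndrome or control) and treatment". Blinding to treatment makes sense only if there are on-treatment samples, but the documents do not say when these are taken.

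The analyses named under Statistical methods are:

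- the primary FMD comparison, with an order-effect check;
- a group comparison: "we will test the interaction between treatment group and the metabolic syndrome (yes/no");
- secondary treatment effects: "we will assess the effects of active therapy on eNOS phosphorylation, insulin sensitivity, and plasma inflammatory markers";
- a first regression: "We will assess the relationship between the change in eNOS phosphorylation and changes in endothelium-dependent vasodilation using linear regression analyses";
- a second regression: "we will examine the relationship between changes in insulin-mediated vasodilation and insulin-sensitivity associated with active treatment";
- MANOVA or MANCOVA, which may take in other outcomes that are not named.

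The supporting regression under Data interpretation again uses eNOS phosphorylation. FFA appears in none of these by name.

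**The concern.** The conclusion is about FFA, but the evidence it calls for is about acipimox. A randomised difference in FMD shows that the drug changed FMD. To say that FFA was the cause, one must at least show that FFA differed between the two visits. The plan takes that step for granted.

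The study's title question is the effect of reducing FFA. Followed as written, the plan could report that FFA impairs endothelial signaling when FFA was the same on both treatments, or was never compared. The reading of a null result has the same weakness. Unchanged vasodilation is to be taken as lack of effect of the agent. Without an FFA comparison, a failure to lower FFA cannot be told apart from lower FFA having no vascular effect.

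**Working it through.** **Does any named analysis supply the missing step?**

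- The secondary treatment effects cover eNOS phosphorylation, insulin sensitivity and inflammatory markers. The examples given extend only the inflammatory markers, and the assay section's heading lists free fatty acids separately from those.
- The regressions relate eNOS phosphorylation to FMD, insulin-mediated vasodilation to insulin sensitivity, and eNOS phosphorylation to vascular or muscle metabolic function. None uses FFA.
- The MANOVA sentence would permit FFA as an outcome but does not commit to it.
- The skin biopsy measures Akt and eNOS. A drug action on the endothelium that bypassed FFA could also raise eNOS phosphorylation, so this step cannot separate the two explanations.

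The gap is therefore real on the text. The arithmetic below does not decide it; it only shows how the rule behaves.

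**Inputs.** From Sample size calculation and Table 2: 30 subjects per group, two-sided alpha 0.05, FMD difference 3% with SD 4%. Assumptions: the SD is that of the within-subject differences, and restored FMD means a significant gain in one group of 30. The documents state neither.

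**Reproducing the plan's figures.** For a paired t-test with n = 30 there are 29 degrees of freedom and the critical value is 2.045. Power is P(|T| > 2.045), where T is noncentral t with noncentrality (effect / SD) × √30.

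| Effect / SD | Noncentrality | Power | Table 2 |
|---|---|---|---|
| 3.0 / 4.0 = 0.75 | 4.11 | 0.978 | .98 |
| 2.5 / 4.0 = 0.625 | 3.42 | 0.911 | .91 |
| 2.5 / 4.5 = 0.556 | 3.04 | 0.837 | .84 |

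A two-sample calculation at 3% and 4% gives 0.83, so Table 2 is for the paired design.

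**Rule as written, FFA unchanged.** If acipimox raises FMD by some other route, the FMD condition is met at the power above: 98% for the planned effect, and 84% to 91% for a 2.5% effect with SD 4.5% to 4.0%. The tissue step follows, and its pass rate cannot be calculated.

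**With an FFA condition (95% confidence interval for acipimox minus placebo below zero), FFA unchanged.** The interval lies below zero at most 2.5% of the time, so both conditions are met at most 2.5% of the time whatever the correlation between the FMD and FFA changes. Simulation (200,000 runs) gives 0.024, 0.024 and 0.021 for correlations of 0, −0.5 and +0.5. At zero correlation the product agrees: 0.978 × 0.025 = 0.024.

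**Cost of the condition when FFA does fall.** At zero correlation, the chance that both conditions are met is 0.978 times the chance that the FFA interval lies below zero.

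| FFA fall (SD of paired differences) | Both conditions met |
|---|---|
| 0.53 | 78% |
| 0.61 | 88% |
| 0.80 | 97% |
| 1.00 | 97.7% |

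**Precision available.** The half-width of the FFA interval is 2.045 / √30 = 0.373 SD in one group of 30 pairs. It is 0.258 SD with 60 pairs pooled, reading the two groups as metabolic syndrome and healthy. The documents give no FFA SD, so none of this can be put in concentration units.

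**The case against.** The strongest reply is that the data are probably there. FFA is assayed in duplicate, blinded to treatment, and nothing forbids comparing it between visits. What is missing is a named analysis and careful wording. That is fair, and it is why the fix is cheap. But measuring FFA does not commit the plan to comparing it, and the rule would still reach its conclusion without the comparison.

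The 98% is Table 2's power under another name, and the 2.5% is one tail of a 0.05 test. That is also fair. The pair illustrates how the rule behaves; it is not a measured rate of false attribution. The 98% also covers only the first of two steps, because tissue testing follows. That step makes the confirmed conclusion harder to reach but says nothing about whether FFA fell.

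A cut-off on the FFA interval is only one choice. A trivial fall can pass and an imprecise larger one can fail. This stands, and the threshold is best left to the sponsor, provided it is set beforehand.

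The documents do not say when FFA is sampled at the treatment visits, so sampling before insulin is a proposal. It rests on the visit already having a pre-insulin period: "Forearm blood flow will be measured in the basal state, and with insulin infusion".

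**Conclusion.** The concern holds and should be fixed. The rule attributes an FMD gain to FFA without requiring that FFA was lower on acipimox, and no FFA treatment comparison is named. The textual finding rests on no assumption.

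The size can be given only conditionally. If FMD improves as planned while FFA is unchanged, the FMD condition for the FFA conclusion is met about 98% of the time, against at most 2.5% once an FFA condition is added. These figures depend on reading restored FMD as a significant gain in one group of 30. The joint figures for a true FFA fall also assume zero correlation between the two changes. No probability is claimed that acipimox acts without lowering FFA. The primary comparison, sample size and power stand as they are.

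**What to change.** 1. **Name the comparison.** Add to the secondary analyses the within-subject acipimox-minus-placebo difference in FFA with its 95% confidence interval, from samples taken at both treatment visits before the insulin infusion. Report it overall and by metabolic-syndrome status, using the repeated-measures model already planned. Optionally, regress change in FMD on change in FFA, adjusting for age and gender as in the eNOS regression.
2. **Make the rule conditional.** Describe an FMD gain as consistent with an FFA effect only if FFA was lower on acipimox in the group for which the gain is claimed. Otherwise report an acipimox effect with mechanism undetermined. State beforehand what counts as lower (for example, an interval wholly below zero) and always show the estimate. An interval that includes zero means undetermined; it does not show that FFA was unchanged.

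**Cost.** One secondary contrast on an assay already planned and one conditional clause. The crossover design, sample size and primary analysis do not change. If visit samples are not already intended, one FFA sample per visit is added. The mechanistic claim becomes harder to make, and even a clear FFA fall is necessary for mediation without proving it.

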Vascular function of the brachial artery will be measured in all subjects as reported previously by the applicants and recommended by a recent task force (56-58) (also see Preliminary Results Section). To assess endothelium-dependent vasodilation, measurements of brachial artery diameter will be made under basal conditions and during reactive hyperemia following five minutes of an ischemic stimulus. Forearm ischemia will be induced by inflating a blood pressure cuff on the upper part of the arm to suprasystolic pressures for 5 minutes. This results in vasodilation of the downstream resistance vessels. Following release of the cuff, there is a 6 to 10-fold increase in flow through the brachial artery, i.e., reactive hyperemia. Flow is a physiologic stimulus that releases nitric oxide from the endothelium. We have found that the maximal increase in brachial artery diameter occurs at one minute of reactive hyperemia and that this dilation is mediated by nitric oxide (56, 57). Endothelium-independent vasodilation will be assessed by measuring brachial artery diameter under basal conditions and 3 minutes following the administration of sublingual nitroglycerin (0.4 mg) (58). Maximal brachial artery dilation occurs 3 to 4 minutes after the administration of sublingual nitroglycerin.

The diameter of the brachial artery will be measured using high resolution B-mode ultrasonography. An ultrasound scanner (Toshiba model Powervision 8000) equipped with a high resolution linear array transducer (7.5 mHz) is used to image the artery and thus enable measurement of its diameter and cross-sectional area. A longitudinal image (parallel to the artery) is acquired just proximal to the antecubital fossa. The transducer is then positioned at 90 degrees to the vessel to acquire an image through the center of the vessel so that the near and far wall interfaces will be clearly discernible. A simultaneous electrocardiographic signal is recorded. The video output and electrocardiographic

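### The rule that reads a flow-mediated dilation gain as an endothelial effect is not linked to the nitroglycerin control, so a rise in both responses yields two unreconciled conclusions

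*Combined protocol and SAP*

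**What the plan says.** The section on conduit vessels measures two responses of the brachial artery. One is FMD, the dilation after five minutes of cuff ischemia. The other is the control: "Endothelium-independent vasodilation will be assessed by measuring brachial artery diameter under basal conditions and 3 minutes following the administration of sublingual nitroglycerin". The study procedures add: "Each visit will include vascular function testing and a forearm skin biopsy". I take this to mean that the nitroglycerin response is obtained under both acipimox and placebo, although the text does not say so in terms.

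Data interpretation then gives two separate rules.

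- **FMD rule.** The trigger is "If flow-mediated vasodilation is restored after an intervention (acipimox) compared with placebo" and the conclusion is "it will be interpreted that FFA impairs endothelial insulin signaling and decreases endothelium-dependent vasodilation". The next sentence attaches a check: "This interpretation will be confirmed by cutaneous tissue testing".
- **Nitroglycerin rule.** "If any intervention increases vasodilation to nitroglycerin, it will be interpreted that the intervention has improved vascular smooth muscle function".

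Statistical methods makes the FMD change the primary endpoint. Of the other outcomes it says: "In secondary analyses, we will assess the effects of active therapy on eNOS phosphorylation, insulin sensitivity, and plasma inflammatory markers". A general multivariate provision adds that "in the analyses, we can include vascular function and other outcomes simultaneously as dependent variables in the models". Neither sentence names the nitroglycerin response.

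**The concern.** By the protocol's own account, flow releases nitric oxide from the endothelium and the resulting dilation is mediated by nitric oxide. That nitric oxide still has to relax smooth muscle, and the plan itself treats the nitroglycerin response as a measure of smooth-muscle function. A higher FMD on acipimox could therefore reflect more endothelial nitric oxide, more responsive smooth muscle, or both. The nitroglycerin measurement is there to help tell these apart, but the FMD rule does not refer to it.

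What is at stake is the mechanistic conclusion drawn from the primary endpoint. The stated hypothesis concerns endothelium-dependent dilation, and the rule goes further, to a statement about free fatty acids and endothelial insulin signaling.

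**Working it through.** **1. The rules side by side.** The plan does not define restored FMD or a nitroglycerin increase numerically. I take each as a difference in favor of acipimox.

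| FMD | Nitroglycerin response | What the rules conclude |
|---|---|---|
| Rises | Does not rise | Endothelial effect, to be confirmed in skin tissue |
| Rises | Rises | Endothelial effect, to be confirmed in skin tissue, and also better smooth-muscle function; nothing reconciles the two |

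The second row is the gap. The nitroglycerin rule adds a conclusion but does not withdraw or qualify the first.

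**2. Whether another provision closes it.**

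- *Skin tissue check.* It is worded as confirmation, with no statement of what follows if it fails. It uses skin microvessels, not the brachial artery. A rise in eNOS phosphorylation could coexist with a smooth-muscle gain.
- *Regression of FMD change on eNOS phosphorylation change.* It controls for age and gender, not for change in nitroglycerin response.
- *Multivariate provision.* It is permissive and does not name nitroglycerin. With both responses as dependent variables it tests a joint difference; it does not make the FMD conclusion depend on the nitroglycerin result.

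**3. The plan's own power figure.** Inputs from the sample size text: 30 subjects per group, difference 3%, standard deviation (SD) 4%, two-sided alpha 0.05. For a paired t-test the noncentrality is (3/4) × √30 = 4.11, which gives power 0.978; Table 2 states .98. All nine cells of Table 2 agree to within 0.01 on this basis. The SD is therefore that of the within-subject difference, and the trial is sized on FMD alone. There is no corresponding figure for nitroglycerin.

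**4. Illustration only.** Suppose acipimox acts purely on smooth muscle and raises FMD by 3 points (SD 4) in 30 subjects. Suppose also that each rule fires when a two-sided 5% paired t-test shows an increase. The nitroglycerin effect and SD are assumed. Results are from 40,000 simulated trials per row, with the two differences uncorrelated:

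| Nitroglycerin gain (points) | SD of difference | Both rules fire | Only FMD rule fires |
|---|---|---|---|
| 3 | 4 | 0.955 | 0.022 |
| 3 | 6 | 0.739 | 0.239 |
| 3 | 8 | 0.502 | 0.475 |
| 1.5 | 4 | 0.503 | 0.475 |
| 1.5 | 6 | 0.258 | 0.719 |
| 1.5 | 8 | 0.163 | 0.815 |

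A correlation of 0.5 changes these by no more than about 0.01. Depending on the assumptions, the endothelial reading would stand alone among the two dilation rules in about 2% to 81% of such trials, before the tissue check.

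**5. Precision of the control.** With 30 pairs, the 95% confidence interval half-width is 2.045 × SD/√30, or 1.5, 2.2 or 3.0 points at SD 4, 6 or 8. If the SD is large, a nonsignificant nitroglycerin difference would not exclude an increase of the same order as the planned 3-point FMD effect. The interval should be reported, not only a test result.

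**6. Scale of a smooth-muscle contribution, under assumption.** If FMD scales in proportion to smooth-muscle responsiveness and placebo FMD is 6%, 8% or 10%, a 10% relative gain adds 0.6, 0.8 or 1.0 points. Producing the whole 3 points would need a gain of 3/6 = 50%, 3/8 = 37.5% or 3/10 = 30%. Both the scaling and the placebo values are assumed.

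**The case against.** The strongest reply is that the plan does not rest the mechanism on FMD alone. Tissue testing measures total and phosphorylated Akt and eNOS, with von Willebrand factor colocalization to place the signal in vascular cells. The eNOS change is related to the FMD change by regression. A pure smooth-muscle effect would not be expected to raise eNOS phosphorylation. The nitroglycerin rule also sits in the same section and presupposes a treatment comparison, and the multivariate provision gives a route to analyze it.

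Much of this stands, and it rules out a stronger reading. A reader might infer that a smooth-muscle effect of acipimox would simply be reported as relief of endothelial impairment. The documents do not support that. A detected nitroglycerin rise would be reported as a smooth-muscle effect alongside the endothelial reading, and the endothelial reading is subject to a tissue check. Nor do the documents suggest that acipimox acts on smooth muscle, so the illustrations above are not evidence that it does.

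What the reply does not supply is a link between the rules, a consequence if the tissue check fails, or a named nitroglycerin analysis.

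Two cautions about the remedy also stand. Barring every endothelial statement when both responses rise would be too strict, because FMD may rise by more than smooth muscle explains. An FMD model adjusted for the nitroglycerin change conditions on a noisy post-treatment variable, so its adjusted difference has no clean causal reading.

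**Conclusion.** The point holds as a defect in the interpretation rules and should be corrected. The FMD rule draws an endothelial conclusion without reference to the endothelium-independent control, and when both responses rise that conclusion stands unqualified beside a smooth-muscle one. The skin check reduces the risk of a wrong mechanistic claim but cannot apportion an FMD gain in the brachial artery.

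The finding rests on the wording of the rules and on the inference that nitroglycerin is given at both visits. Its practical size is unknown: the documents give no placebo FMD and no nitroglycerin effect or SD, so every magnitude above is illustrative. The primary endpoint, its test and the sample size are unchanged.

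**What to change.** 1. In Statistical methods, name the acipimox-minus-placebo difference in nitroglycerin response as a planned secondary analysis, in the same crossover model as FMD, reported with its 95% confidence interval.
2. In Data interpretation, attribute an FMD gain specifically to the endothelium only after reading it jointly with the nitroglycerin estimate and interval and the tissue result. State that if both dilations rise, the result is reported as improved conduit dilator function, with a smooth-muscle contribution not excluded. The documents give no basis for a numerical margin, so this should be worded as a joint reading, not a pass/fail test.
3. Label any FMD model adjusted for change in nitroglycerin response as exploratory, and say that it conditions on a post-treatment variable.

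The cost is wording and one standard model on measurements already planned, with no new procedure and no extra subjects. The downside is that an FMD gain accompanied by a nitroglycerin gain, or by a wide nitroglycerin interval, will support a weaker mechanistic claim. A wide interval could have that effect even when there is no smooth-muscle effect, because the trial was not sized for this comparison.
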